5 AIMS AND OBJECTIVES

5.1 AIMS

This trial aims to answer the following questions -

Does the use of serum markers of liver fibrosis:

- a) permit earlier detection of liver cirrhosis in patients with Chronic Liver Disease (CLD) to allow earlier interventions?
- b) affect the process of care, through a) increased use of beta-blockers/band ligation of varices to prevent haemorrhage/HCC; b) increased use of endoscopy and ultrasound/AFP's to detect HCC at a surgically curable stage; and c) effective early treatment to normalise Liver Function Tests (LFT's) in patients with Hepatitis B and Hepatitis C.
- c) result in patient benefit through improved survival and reduced liver-related morbidity and mortality?
- d) improve the cost-effectiveness of the management of end-stage liver disease?

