13.1.1 Portal Hypertension

All patients with diagnosis of cirrhosis should have an oesophagogastroduodenoscopy (OGD) as screening for varices within 3 months of diagnosis as defined by an ELF score ≥ 9.5 or by clinical criteria, unless they have had an OGD in the last 18 months prior to the diagnosis of cirrhosis.

Timing of initial oesophagogastroduodenoscopy (OGD) following a diagnosis of cirrhosis:

- If the patient underwent OGD within 18 months prior to being diagnosed as cirrhotic, the next OGD should be performed **within 18 months of the previous OGD** unless clinically indicated sooner.
- If the patient did not have an OGD within 18 months prior to being diagnosed as cirrhotic, they should undergo OGD screening for oesophageal varices **within 3 months** of diagnosis of cirrhosis.

Timing of subsequent OGDs after a diagnosis of cirrhosis:

- If the previous OGD did not identify oesophageal varices, subsequent OGDs should be repeated **every 18 months from the previous OGD**.
- If small oesophageal varices at OGD are identified, OGDs should be repeated **every 6 months** to look for variceal progression.
- For large oesophageal varices currently being treated, the timing of subsequent OGDs can be dictated by local guidance.

Primary prophylaxis for oesophageal varices

- moderate or large oesophageal varices should be banded as primary prophylaxis
- banding should be repeated until the varices are obliterated with banding at weekly visits
- alternatively patients can be treated with non-cardioselective beta-blockers

Secondary prophylaxis for oesophageal varices

- bleeding oesophageal varices should be obliterated with banding at weekly visits
- in addition to band ligation, patients should be considered for treatment with beta-blockers unless contraindicated

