14 ASSESSMENTS & DATA COLLECTION

Trial data will be recorded by research staff on Case Report Forms (CRFs) and submitted to the CTRU at the address given in the Investigator Site File. Details on the schedule of CRFs, data to be collected, and guidance on the completion of CRFs will be given to individual sites when approval to participate in the trial is obtained.

Participating sites will be expected to maintain a file of essential trial documentation (Investigator Site File) which will be provided by CTRU, and keep copies of all completed CRFs for the trial.

A tabulated summary of all local and central assessments is provided in Tables 2-5.

ELUCIDATE is a pragmatic trial enrolling patients with known chronic liver disease who will undergo a number of tests as part of their routine care. It is important that the results of these routine tests are recorded on the CRFs. In addition, patients will be asked to provide blood samples for non-invasive assessment of liver fibrosis (ELF tests) that are additional to routine care, form part of the protocol and are fully funded by the research grant.

Addresses to which the samples should be sent and procedures are provided in the Site Specific Operations Document and the inside of the back cover.

Where applicable (e.g. copies of laboratory reports), *it is the responsibility of staff at research sites to obliterate all personal identifiable data on any hospital reports, letters, etc. prior to sending to the CTRU.* Such records should only include trial number, initials, and date of birth to identify the patient.

REGISTRATION VISIT

Table 2 details information to be recorded at registration. The baseline data must have been collected in the month prior to registration or at the registration visit as follows (note ELF test must be performed at the registration visit):

- Physical examination
- Demographics
- Medical history (including details of concomitant disease)
- ELF test
- Health questionnaires (EQ-5D™ and SF-12v2™)* – patients to self-complete at the visit

*EQ-5D™ Health Questionnaire © 2009 EuroQol Group. EQ-5D™ is a trade mark of the EuroQol Group. SF-12V2™ Health Survey © 2000 by QualityMetric Incorporated – All rights reserved. SF-12V2™ is a trademark of QualityMetric Incorporated.

Table 2. Assessments to be performed at Registration.

X = compulsory.

Assessment	Registration
History	X
Exam	X
EQ-5D™/SF12v2™	X
ELF	X

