14.2.1 Follow-up assessments

At each follow up visit all patients will undergo:

- Physical examination (weight, vital signs)
- Medical history (including details of concomitant disease and medication)
- Blood tests (simple LFTs, Platelets, Albumin, and clotting)

- Health questionnaires (EQ-5D™ SF-12v2™ and Health Usage Questionnaire)- patients to self complete at visit

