17.2 SECONDARY ENDPOINTS

- Time from diagnosis of cirrhosis (by ELF or clinical means) to incidence of first severe complication

* Milan criteria: One lesion less than 5cm, up to 3 lesions smaller than 3cm, no extrahepatic manifestations, no vascular invasion.

- Time from randomisation to diagnosis of cirrhosis by ELF or clinical means (to allow instigation of prophylaxis and screening)
- Process outcomes, namely:
 - treatment with beta-blockers/band ligation (BB/BL) of varices
 - use of endoscopy and ultrasound/AFP tests
 - treatment to normalise LFTs in patients with Hepatitis B and Hepatitis C.
- Detection and timing of complications following cirrhosis, including:
 - Detection of small varices
 - Detection of large varices
 - Incidence of treatable hepatocellular cancer (HCC)
- All causes of mortality
- Specific liver-related morbidity
- Economic evaluation of the ELF test in the early detection of cirrhosis and as such in the initiation of measures to reduce the incidence of severe complications following cirrhosis.
- Quality of Life (QoL)
- Proportion of non-randomised patients (ELF < 8.4) who go on to develop cirrhosis (diagnosed by clinical means) within the follow-up period.

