9.49 to develop cirrhosis during the 24 months of recruitment and 36 months of follow-up, which when added to the 185 patients who present with cirrhosis in this arm through having an ELF >9.49 gives a total of 216 patients developing cirrhosis in the ELF arm. In the control arm we expect 185 patients to have an ELF >9.49 and we expect approximately 46 of these to develop severe complications after 24 months of recruitment and 36 months of follow-up and therefore be diagnosed as cirrhotic at that point. We expect a further one third of these 185 patients to be diagnosed as cirrhotic on clinical grounds which adds another 62 patients. In addition we estimate that approximately 10% of the 315 patients with an ELF score between 8.4 and 9.49 will progress to cirrhosis on clinical grounds. This gives a total of 139 patients developing cirrhosis in the control arm. Therefore we are expecting approximately 31/216 patients encountering severe complications in the ELF arm subsequent to development of cirrhosis compared with approximately 52/139 in the control arm, after 24 months of recruitment and 36 months of follow-up. With a type I error rate of 5% we would have >99% power to detect this difference in this secondary endpoint.

The trial as its original size was thus well powered (at least 90% for the primary endpoint from randomisation with an additional 5 years of follow-up) to show that this ELF monitoring policy will be of real clinical benefit.

Following the recommendation by the funding body to close the trial to recruitment, it is anticipated that by the time the resulting protocol amendment is approved and implemented, approximately 700 patients will have been randomised. Based on this, and with follow-up continuing until July 2014, the trial will have adequate statistical power to report on changes in the process of the care which are critical to the prevention of gastro intestinal haemorrhage and Hepatocellular Carcinoma (HCC) in patients with chronic liver disease who are monitored using the ELF test.

The first process of care would be the use of beta-blockers/band ligation (BB/BL) of varices to prevent haemorrhage. The ELUCIDATE trial will not report the major liver events and survival within the period of the Programme. However, recruitment as planned will be sufficient for these analyses if the patients are followed for a further five years and additional funding is being sought to complete this work.

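### The lead process-of-care outcome, beta-blocker or banding use, is meant to measure prevention of haemorrhage but as worded also counts treatment given after a variceal bleed

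*Protocol*

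**What the plan says.** Section 17.2 defines the process outcome as "treatment with beta-blockers/band ligation (BB/BL) of varices". Neither that section nor the study definitions in 17.3 says whether the treatment must come before a bleed.

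The purpose is stated more narrowly elsewhere. Section 5.1 asks whether ELF testing leads to "increased use of beta-blockers/band ligation of varices to prevent haemorrhage/HCC". Section 18.1 says "The first process of care would be the use of beta-blockers/band ligation (BB/BL) of varices to prevent haemorrhage" and then powers this outcome for the shortened trial: 5% in the ELF arm against 1% in the control arm, 700 patients, follow-up to July 2014, power 86%.

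Section 13.1.1 describes two settings for the same treatments:

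- **Primary prophylaxis:** "moderate or large oesophageal varices should be banded as primary prophylaxis", and "alternatively patients can be treated with non-cardioselective beta-blockers".
- **Secondary prophylaxis:** "bleeding oesophageal varices should be obliterated with banding at weekly visits", with beta-blockers to be considered in addition.

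Section 17.1 puts variceal haemorrhage first among the severe complications that make up the primary endpoint.

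**The concern.** Banding of varices that have bled is band ligation of varices, so it meets the endpoint as written. The same patient is then a failure on the primary endpoint and a success on the outcome meant to show prevention. Section 13.1.1 already separates the two settings, but the endpoint does not use that separation.

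The trial expects 40% fewer complications in the ELF arm, so post-bleed treatment should occur more often in controls and narrow the difference between arms. This matters because 18.1 says major liver events will not be reported within the Programme. Beta-blocker or banding use is the outcome for which the shortened trial gives worked rates and power. With so few control events predicted, a handful of post-bleed treatments could form a large share of them.

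**Working it through.** **Inputs**

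- Patients per arm: 700 / 2 = 350 (18.1; 1:1 allocation in 12.2). Two-sided 5% level (19.2).
- Predicted use: 5% ELF, 1% control (18.1), that is 350 × 0.05 = 17.5 and 350 × 0.01 = 3.5 patients.
- Variceal bleeds: 3% at 36 months in standard-arm patients with ELF ≥ 9.5 (18.1).
- Share of patients at that ELF level: 37% as stated in 18.1 (80/225 is 35.6%).
- Reduction in complications in the ELF arm: 40% (18.1).
- Mean follow-up to July 2014: not given. I take 24 months as an assumption, with 36 months as an upper bound. As a rough check, 19.1 describes July 2014 as close to 3 years of recruitment and follow-up, and the last randomisation is due by 30/04/2013, about 14 months before. Even accrual gives (36 + 14)/2 = 25 months.
- Every bleeder is taken to receive banding or a beta-blocker (assumption, relaxed below).

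**Step 1: the protocol's own figure.** Power = Φ[(p1 − p2 − 1.96·s0)/s1], where s0 is the pooled and s1 the unpooled standard error of the difference. For 5% v 1%, s0 = 0.01290 and s1 = 0.01281, so (0.04 − 0.02527)/0.01281 = 1.150 and power is 87%. Fisher's exact test gives 86.9%. The stated 86% is reproduced.

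**Step 2: expected bleeders.**

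- 36 months: control 0.03 × 0.37 = 1.11%, or 3.9 of 350. ELF 1.11% × 0.6 = 0.67%, or 2.3 of 350.
- 24 months: control 1.11% × 24/36 = 0.74%, or 2.6 of 350. ELF 0.74% × 0.6 = 0.44%, or 1.6 of 350.

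**Step 3: post-bleed treatment on top of 5% v 1%.**

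| Mean follow-up | ELF | Control | Power |
|---|---|---|---|
| none added | 5.00% | 1.00% | 87% |
| 24 months | 5.44% | 1.74% | 75% |
| 36 months | 5.67% | 2.11% | 68% |

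If a quarter of bleeders die untreated (4.3 gives 25% mortality for variceal bleeding), the 24-month control addition is 0.74% × 0.75 = 0.56% and power is 78%.

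**Step 4: post-bleed treatment already inside 5% v 1%.** At 24 months, the pre-bleed rates are 5.00 − 0.44 = 4.56% and 1.00 − 0.74 = 0.26%. Power for the pre-bleed outcome is then 96%. At 36 months it cannot all lie inside the control figure if every bleeder is treated, because 3.9 exceeds 3.5.

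**The case against.** The best counter-argument is that the power loss double-counts. The control 1% is one tenth of all controls diagnosed with cirrhosis, with no pre-bleed condition. Section 18.1 also treats controls who have a severe complication as diagnosed with cirrhosis at that point. On that logic bleeders already sit inside the 1%, so 75% and 68% are conditional figures and not predictions. This stands. It does not remove the problem: if post-bleed treatment is inside the 1%, much of the predicted control count may not be prevention at all.

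Section 19 leaves analysis detail to the SAP, which is not shown and may split use by bleed. That is possible, but the protocol's endpoint is still wider than the protocol's stated purpose.

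Three stronger readings are tempting, and the document does not support them.

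- **Beta-blockers taken for other reasons are counted too.** The registration history names only concomitant disease ("Medical history (including details of concomitant disease"), while the follow-up history adds medication ("Medical history (including details of concomitant disease and medication"). But the words 'of varices' limit the indication, and 7.1.2 excludes patients with varices on imaging or a previous variceal bleed. The history items are not an exhaustive CRF list, and the protocol gives no background rate from which to compute a loss.
- **Only non-cardioselective agents should count.** Section 13 permits documented local protocols, so 13.1.1 does not fix the agent for the whole trial.
- **The wording could create a false claim for ELF.** On the trial's own hypothesis, post-bleed use dilutes the contrast; it does not inflate it.

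**Conclusion.** The endpoint in 17.2 is worded more broadly than the prevention claim it serves: treatment after a bleed, itself a primary-endpoint event, counts as success. This follows from the text and needs no assumption about rates.

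The effect on the result is dilution of uncertain size. About 2.6 control patients (24 months, assumption) to 3.9 (36 months, upper bound) could be treated after a bleed, against 3.5 predicted in total. Power falls from about 87% to 75% or 68% only if this use is additional to 5% v 1%. If it is already included, restricting to pre-bleed use raises power. Either way, the restricted outcome gives the sharper contrast and matches the stated aim. The figures rest on the protocol's 3%, 37% and 40%, on bleeds accruing evenly over time, and on bleeders being treated. The protocol's 86% is correct for the rates it assumes.

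**What to change.** Define the outcome as the first beta-blocker or band ligation given for varices after randomisation and before any variceal haemorrhage, with all randomised patients as denominator. Report beta-blocker or banding started after a bleed separately, as secondary prophylaxis. Do not restrict by agent class, since local protocols are allowed.

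The data are largely planned already: confirmed variceal haemorrhage as a timed primary-endpoint component (17.1), medication at each follow-up visit (14.2.1), and varices with or without bleeding on the CRFs (15.2.1). Recording the indication for any beta-blocker on the CRF would be a useful but optional clarification.

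The cost is one counting rule in 17.2, carried into the SAP, and a slightly lower event count. It changes only what is counted, not how any patient is managed.

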17.3 STUDY DEFINITIONS

- Small varices are defined as varices that flatten with insufflations or minimally protrude into the oesophageal lumen⁴²
- Large varices are defined as varices that protrude into the oesophageal lumen and touch each other (presence or confluence), or that fill at least 50% of the oesophageal lumen⁴².
- Hepatocellular cancer classifications will follow standard guidelines^{21,40}

18 STATISTICAL CONSIDERATIONS

18.1 SAMPLE SIZE

The RCT is testing the hypothesis that if we monitor patients with chronic liver disease using the ELF score, we will detect liver cirrhosis earlier, and as a result there will be fewer severe complications as well as improvements in other important patient outcomes. We are therefore aiming to show that the incidence of severe complications following cirrhosis is less in the ELF arm.

It was anticipated that the trial would recruit over 24 months with an additional 30 months follow up, and with an additional 39 months long-term follow-up for the primary endpoint of time from randomisation to incidence of first severe complication (taking us to 5 years after the end of the programme grant). Previous studies⁴³ have led us to anticipate that in the standard arm, at 36 months, in patients with an ELF ≥ 9.5 , we will observe severe complications of the order of 3% variceal bleeds, 10% liver decompensation, 1.5% requirement for liver transplantation, 7.5% liver related mortality giving a 22% incidence of potentially preventable undesirable clinical endpoints at 36 months in these patients.

Previous data⁹ has illustrated that approximately 20% of patients will have varices suitable for therapy. Such therapy has a large effect on the progression of these varices (for instance a reduction from 37% progressing to 11%); on the risk of bleeding from these varices (reduced from 30% to 14% in patients with medium to large varices); and on mortality at 36 months (reduced from 7% to 2% over 24 months⁹). Based on this prior data we hypothesise that we could reduce the incidence of the undesirable clinical endpoints of cirrhosis by 40% in the ELF arm.

Eighty out of the first 225 (37%) patients have presented with an ELF >9.49 . We are aiming to recruit 500 patients per arm, so we would expect 185 control arm patients to have an ELF >9.49 . With a 22% incidence rate of severe complications at 36 months, 24 months of recruitment and 30 months of follow up the expected number of events in these 185 patients can be calculated, using the method described by Collett⁴⁴ for sample size estimates based on exponential survival distributions (more details of which can be seen in the SAP). This produces an estimate of 46.4 events in these 185 control arm patients. We would also expect approximately 10% of the remaining 315 control arm patients to progress to cirrhosis on clinical grounds and to subsequently have a similar probability of then developing severe complications. This adds another 5.1 estimated events from this group, giving a total of approximately 52 estimated events in the control arm. We expect to reduce this number by 40% in the ELF arm, giving a total number of estimated events in this arm of 31. The median survival times, assuming negative exponential survival distributions, that would produce these numbers of events for the control and ELF arms with 24 months of recruitment and 30 months of follow up are 22.5 and 39.1 years, respectively. These figures can be used to calculate the power to detect such an effect size, which, with a type I error rate of 5%, gives a figure of 70%. However, if follow-up is continued until five years beyond the end of the programme grant, i.e. 69 months of follow-up rather than 30, the power to detect this effect size increases to just over 90%.

To calculate the power, with these 1000 patients, to detect a difference in the secondary endpoint of numbers of patients encountering severe complications subsequent to being detected with cirrhosis, we also need to estimate the numbers of patients developing cirrhosis in the two arms. We expect approximately 10% of the 315 patients with an ELF score between 8.4 and

9.49 to develop cirrhosis during the 24 months of recruitment and 36 months of follow-up, which when added to the 185 patients who present with cirrhosis in this arm through having an ELF >9.49 gives a total of 216 patients developing cirrhosis in the ELF arm. In the control arm we expect 185 patients to have an ELF >9.49 and we expect approximately 46 of these to develop severe complications after 24 months of recruitment and 36 months of follow-up and therefore be diagnosed as cirrhotic at that point. We expect a further one third of these 185 patients to be diagnosed as cirrhotic on clinical grounds which adds another 62 patients. In addition we estimate that approximately 10% of the 315 patients with an ELF score between 8.4 and 9.49 will progress to cirrhosis on clinical grounds. This gives a total of 139 patients developing cirrhosis in the control arm. Therefore we are expecting approximately 31/216 patients encountering severe complications in the ELF arm subsequent to development of cirrhosis compared with approximately 52/139 in the control arm, after 24 months of recruitment and 36 months of follow-up. With a type I error rate of 5% we would have >99% power to detect this difference in this secondary endpoint.

The trial as its original size was thus well powered (at least 90% for the primary endpoint from randomisation with an additional 5 years of follow-up) to show that this ELF monitoring policy will be of real clinical benefit.

Following the recommendation by the funding body to close the trial to recruitment, it is anticipated that by the time the resulting protocol amendment is approved and implemented, approximately 700 patients will have been randomised. Based on this, and with follow-up continuing until July 2014, the trial will have adequate statistical power to report on changes in the process of the care which are critical to the prevention of gastro intestinal haemorrhage and Hepatocellular Carcinoma (HCC) in patients with chronic liver disease who are monitored using the ELF test.

The first process of care would be the use of beta-blockers/band ligation (BB/BL) of varices to prevent haemorrhage. The ELUCIDATE trial will not report the major liver events and survival within the period of the Programme. However, recruitment as planned will be sufficient for these analyses if the patients are followed for a further five years and additional funding is being sought to complete this work.

Power calculations are based on our hepatology estimates of the identification of large varices in cirrhotic patients and the expected identification of cirrhotic patients in the ELF and control arms. Once identified as cirrhotic, approximately 10% of patients are predicted to be treated with beta-blockers/band ligation (BB/BL) of varices.

In the ELF arm, current estimates suggest 40% of patients will be diagnosed with cirrhosis initially, and 10% diagnosed during follow up to July 2014. Therefore in this total of 50% of patients, we would predict the use of BB/BL in 1 in 10, i.e. 5% of the total. In the control arm, conservatively we predict the clinical diagnosis of cirrhosis to be made in under 10% of the patients by July 2014: therefore 1% of the total would receive BB/BL. Based on the

assumption of 700 patients randomised at the end of the recruitment period and follow up until July 2014, power is 86%. We will have approximately 40% power for this endpoint at the interim analysis in summer 2013. Similarly with the additional follow up until July 2014, we will have good power to show changes in the frequency of endoscopy and ultrasound/AFP's to detect HCC at a surgically curable stage and also to detect changes in Liver Function Tests (LFT's) in patients with Hepatitis B and Hepatitis C. The power to detect changes in the frequency of endoscopy and ultrasound/AFP's should be very good (>90%) at the interim analysis in summer 2013, and the power to detect changes in LFTs should be of the order of 60% for Hepatitis B patients and 90% for Hepatitis C patients.

As previously mentioned we will also have enough patients to have good statistical power (approximately 80%) after five years further follow up for the detection of changes in the primary endpoints of the existing trial which are major liver events and survival. These endpoints will only be delivered with long follow up of five years. This will capture major liver events and long term consequences of ELF testing, survival and health economics.

The detailed information collected within the Programme and the impact of ELF on the process of care will provide detailed information that will be essential in the interpretation of the long follow up and the impact of ELF testing on major liver events and survival.

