7.1.2 Exclusion criteria

- unable to provide consent
- Imaging, histological or laboratory diagnosis of cirrhosis (other than ELF) /portal hypertension as evidenced by any one of the following:
 - Imaging evidence of portal hypertension (splenomegally, varices or ascites)
 - Liver biopsy diagnostic of cirrhosis (Ishak F6 or equivalent)
 - Thrombocytopenia (platelets $< 100 \times 10^9/L$)
 - Hypoalbuminaemia (albumin $< LLN$)
- Acute Liver Injury or Acute Liver failure (hepatic dysfunction < 6 months in duration)
- An ongoing or previous episode of hepatic decompensation (acute on chronic liver failure) including:
 - encephalopathy, variceal bleeding, ascites, jaundice or liver synthetic dysfunction
- An Established diagnosis of hepatocellular cancer or elevated alpha feto-protein without investigation to exclude hepatocellular cancer
- Patient being treated with heparin (ELF test cannot be performed).
- Previously screened and found ineligible for the ELUCIDATE Trial

Note that

- HIV co-infection is NOT an exclusion criterion.
- The solitary finding of a coarse appearing liver on imaging is not an exclusion criterion.

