14.5 CESSATION OF FOLLOW-UP

Cessation of follow-up should only occur under the following circumstances:

- Patient has completed the final follow-up visit at 30 months post-randomisation
- Patient undergoes liver transplantation
- Patient has an episode of severe encephalopathy of (Westhaven criteria 3-4) or otherwise loses capacity to consent
- Patient dies
- Patient withdraws from trial

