17 ENDPOINTS

17.1 PRIMARY ENDPOINT

- Time from randomisation to occurrence of first severe complication

Severe complications are defined by:

1. Variceal haemorrhage confirmed by one of the following:
 - a) visualisation through endoscopy
 - b) imaging
 - c) post-mortem
2. Spontaneous bacterial peritonitis:
Ascites confirmed by:
 - a) Imaging and/or
 - b) aspiration*and* infection confirmed by:
 - a) microscopy and/or
 - b) culture
3. Hepatocellular cancer (HCC) beyond the Milan criteria^{* 40, 41}
N.B. For the purposes of the trial cases of HCC falling within the Milan criteria are not regarded as endpoints as they are regarded as treatable.
4. Encephalopathy - grade 3 or 4 defined using the Westhaven criteria (Appendix 1)⁴².
5. Liver-related mortality. Any of the following:
 - a) Any mention of liver disease in part one of the death certificate
 - b) death due to hepatocellular cancer (HCC)
 - c) death due to liver failure
 - d) death due to bleeding from portal hypertension
 - e) death due to hepato-renal syndrome
 - f) death due to sepsis occurring as a result of chronic liver disease
 - g) death due to spontaneous bacterial peritonitis
 - h) death due to encephalopathy

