18.2 PLANNED RECRUITMENT RATE

We aimed to randomise up to 1000 patients within 24 months of recruitment. The power for the primary endpoint of time to occurrence of liver related outcomes from randomisation is sufficiently great that we will still be very well powered even if there is a substantial drop out rate of as high as 15%-20%. The recruitment target is approximately 42 patients per month. In order to randomise 1000 patients into the trial, it is estimated from previous research³⁶ that approximately 2160 patients will have to be registered to undergo screening with the ELF test (to have 1000 patients meet the randomisation inclusion criteria of $ELF \geq 8.4$).

Following the recommendation by the funding body to close the trial to recruitment, it is anticipated that by the time the resulting protocol amendment is approved and implemented, approximately 700 patients will have been randomised.

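### The 22% control rate behind the primary-endpoint power (Protocol 18.1) belongs to a different composite from the endpoint in 17.1, so the 70%, 90% and 80% powers are unsupported for that endpoint

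*Protocol*

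**What the plan says.** Section 18.1 gives the expected 36-month experience of standard-arm patients with ELF ≥ 9.5 as "3% variceal bleeds, 10% liver decompensation, 1.5% requirement for liver transplantation, 7.5% liver related mortality giving a 22% incidence". It uses that 22% to obtain 46.4 events in 185 control patients, adds 5.1 from the lower-ELF group, rounds to 52, and takes 40% off to reach 31 in the ELF arm. The stated power is 70% with 1000 patients and 30 months of follow-up, and just over 90% at 69 months. After early closure at about 700 patients, the section claims "good statistical power (approximately 80%) after five years further follow up".

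The effect is introduced after figures for variceal therapy: "we hypothesise that we could reduce the incidence of the undesirable clinical endpoints of cirrhosis by 40% in the ELF arm".

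Section 17.1 defines the primary endpoint as time to the first of five events: confirmed variceal haemorrhage, SBP, "Hepatocellular cancer (HCC) beyond the Milan criteria", encephalopathy of grade 3 or 4, and liver-related death. Section 14.5 lists "Patient undergoes liver transplantation" among the reasons for stopping follow-up. The only description of decompensation in the protocol is in 7.1.2: "encephalopathy, variceal bleeding, ascites, jaundice or liver synthetic dysfunction".

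On drop-out, 18.2 says "we will still be very well powered even if there is a substantial drop out rate of as high as 15%-20" per cent.

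**The concern.** A power statement for a time-to-first-event endpoint needs the rate of first events of that endpoint. The components of the 22% do not match 17.1:

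- Transplantation (1.5 points) is counted in the rate but is not an event, and it ends scheduled follow-up.
- Decompensation (10 points) is the largest item. On the 7.1.2 description it includes ascites, jaundice and synthetic dysfunction, none of which is an event by itself. Only SBP and grade 3-4 encephalopathy would qualify beyond the separately listed bleeds.
- HCC beyond Milan is an event but is not in the sum.
- Four percentages are simply added. The total is a first-event rate only if no patient appears in two components, and the section does not say so.

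The 40% reduction is presented as based on variceal-therapy data, but no step leads from those data to 40%.

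Section 18.1 relies on these powers to say that recruitment suffices for the primary question after five more years, while further funding is sought. If the rate for the defined endpoint is well below 22%, a null result at five years would be less informative than the protocol suggests.

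**Working it through.** **Reproducing the stated figures.** Exponential survival with uniform accrual over a months and further follow-up f months:

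P(event) = 1 − [exp(−λf) − exp(−λ(a+f))]/(λa)

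With λ = −ln(0.78)/36 = 0.0069, a = 24 and f = 30, P = 0.2508, and 185 × 0.2508 = 46.4 events, as stated. The printed medians of 22.5 and 39.1 years give a hazard ratio of 22.5/39.1 = 0.575. Schoenfeld power (two-sided 5%) is Φ(½·√d·|ln HR| − 1.96), where d is total events:

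- 500 per arm, 30 months: d = 51.0 + 30.1 = 81.1, power 70.1%.
- 500 per arm, 69 months: d = 93.8 + 56.4 = 150.2, power 92.3%.
- 350 per arm, 69 months: d = 65.7 + 39.5 = 105.1, power 80.9%.

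So the calculation is sound given its inputs. Solving the medians for an exact 40% cut (51.5 and 30.9 events) gives a hazard ratio of 0.587 and powers of 68%, 91% and 79%. That version is the base for the table.

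**Varying the control rate.** The 40% reduction and the document's 5.1 : 46.4 ratio for the lower-ELF group are kept.

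| 36-month rate | Reading | 1000 pts, 30 mo | 1000 pts, 69 mo | 700 pts, 69 mo |
|---|---|---|---|---|
| 25% | 3 points above the stated rate, to allow for omitted HCC (assumption) | 74% | 94% | 84% |
| 22% | as stated | 68% | 91% | 79% |
| 20.5% | transplant removed | 65% | 89% | 76% |
| 15.5% | transplant and half of decompensation removed (assumption) | 52% | 79% | 64% |
| 10.5% | bleeds and liver deaths only (3 + 7.5) | 38% | 62% | 47% |

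The 10.5% row is a floor, given that bleeds and deaths do not overlap: it counts no decompensation and no HCC. In the other direction, section 4.1 puts HCC in cirrhosis at about 5% a year, or 1 − 0.95³ = 14% by 36 months, with an unstated share beyond Milan.

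**The 40% reduction.** A cut of 40% in 22 points requires 8.8 points. Section 18.1 cites bleeding falling from 30% to 14% (relative reduction 16/30 = 53%) and mortality from 7% to 2% (5/7 = 71%; the text labels this both as at 36 months and as over 24 months). About 20% of patients are said to have varices suitable for therapy.

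- Full effect on all bleeds and all liver deaths: 3 × 0.533 + 7.5 × 0.714 = 1.6 + 5.4 = 7.0 points; 7.0/22 = 32%.
- Mortality effect limited to the 20%: 1.6 + 0.2 × 5.36 = 2.7 points; 2.7/22 = 12%.
- Absolute reductions applied within the 20%: 0.2 × 16 + 0.2 × 5 = 4.2 points; 4.2/22 = 19%.

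At a 22% rate with 700 patients and 69 months, a 32% reduction has 57% power, a 20% reduction 25% and a 12% reduction 11%.

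**Drop-out.** If drop-outs contribute no data, d is multiplied by 0.85 or 0.80. On the printed medians:

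- 700 patients, 69 months: 80.9% falls to 74% and 72%.
- 1000 patients, 30 months: 70.1% falls to 63% and 60%.
- 1000 patients, 69 months: 92.3% falls to 88% and 86%.

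**The case against.** The strongest reply is that nothing has been miscalculated. The four components do add to 22, and all three powers reproduce to within about two points. The only component certain to be outside the endpoint is transplantation, and removing it costs two to three points. The 7.1.2 list is an exclusion criterion, not the source study's definition of decompensation, and it includes encephalopathy and variceal bleeding, so some of the 10 points may qualify. Omitted HCC pushes the rate up. All of this stands, so the rate range must run both ways.

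The 40% is labelled a hypothesis, and the strategy also includes peritonitis prophylaxis, HCC surveillance and hepatitis treatment. The 12-32% check credits none of these and keeps decompensation in the denominator. On a 10.5-point base the same figures give 7.0/10.5 = 66% or 2.7/10.5 = 25%, which bracket 40%. The check therefore shows that the stated basis does not lead to 40%, not that 40% is wrong.

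The drop-out sentence was written for 1000 patients and roughly holds there at 69 months. Flagging with routine NHS sources (6.3 and 11) may also capture events in patients who stop attending.

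Three stronger readings are tempting but unsupported:

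- **Patients are counted twice.** Overlap is plausible, since 7.1.2 places bleeding under decompensation while 18.1 lists bleeds separately. But 18.1 does not say whether its components are first events, and the source is not available.
- **The 70%, 80% and 90% will not be achieved.** The corrected rate is unknown and could lie on either side of 22%.
- **About one event is averted per extra patient given beta-blockers or banding.** This would set a treatment forecast of 5% v 1% (700 patients, to July 2014) against 52 v 31 events (1000 patients, 24 + 30 months, any mechanism). The bases differ.

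**Conclusion.** The mismatch is real and visible within the protocol: the 22% includes transplantation and undifferentiated decompensation, leaves out HCC beyond Milan, and is a plain sum with no statement that the components are exclusive. The stated powers are correct consequences of their inputs but unsupported for the endpoint in 17.1. For the 700-patient, 69-month case the plausible span is wide, from 47% at the floor to about 84% at a rate of 25%, against the stated figure of about 80%. These figures assume exponential survival, a 40% reduction, 24 months of accrual and the document's own ratio for the lower-ELF group. The basis of the 40% also needs stating, because the data cited for it do not produce it on the 22% base without some further benefit. The drop-out assurance in 18.2 is too strong for 700 patients: about 72-74% if drop-outs contribute nothing, with a smaller loss if routine data capture their events.

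**What to change.** In 18.1, rebuild the 36-month control rate from the five components of 17.1, counting each patient once at the first qualifying event. Exclude transplantation and decompensation that does not meet 17.1, and include HCC beyond Milan. If the source study does not allow this, say so and give a range. State what the 40% rests on for that base, including any benefit assumed beyond variceal therapy, and resolve the 24- versus 36-month label on the mortality figure. Restate power at 700 patients as a grid of control rates on both sides of 22% (for example 10% to 25%) by reductions (for example 15% to 40%).

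In 18.2, replace the drop-out sentence with figures for 700 patients at 15% and 20% loss, saying whether events in drop-outs are expected from routine data.

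The cost is a recalculation and some redrafting. Nothing changes for patients or sites, and recruitment is unaffected. The price is that the stated power becomes a range, whose lower part will be less favourable in the funding case.
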